Study Protocol and Statistical Analysis Plan

Title: The prevalence and risk factors of coagulopathy in pediatric patients undergoing surgery for epilepsy: a retrospective cohort study

Date: 2022-11-02

Background:

Epilepsy is a common disease of the nervous system with severe consequences. Epidemiological surveys have shown that the prevalence of epilepsy in China is approximately 0.4–0.7%, comprising 7–10 million patients with epilepsy(1), most of whom are children(2). Although most symptoms of epilepsy can be controlled with the use of anti-seizure medications (ASMs), there are still a few patients who cannot achieve satisfactory seizure control with such medications or cannot tolerate their side effects, thus requiring surgical treatment. Surgical treatment of epilepsy has been recognized as a valuable treatment option for carefully selected patients to achieve better seizure control and quality of life(3). Compared to adults, children with epilepsy with indications for surgery usually have a better prognosis after surgical treatment(4–8). Many children undergoing surgery for epilepsy have a long history of using ASMs. Moreover, ASM therapy usually consists of multiple varieties of drugs, thereby bringing significant attention to the side effects of ASMs, especially those that may be relevant in the perioperative surgical setting.

ASMs have been associated with multiple adverse effects on platelets and the coagulation system(9). Valproic acid (VPA), one of the most commonly used traditional ASM, has been reported to cause multiple hematologic abnormalities, including thrombocytopenia, platelet aggregation dysfunction, fibrinogen (FBG) depletion, bone marrow suppression, decreased factor XIII, and acquired von Willebrand disease(10–17). However, the wide use of novel ASMs in recent decades has led to decreased reports of adverse events. The hematologic consequences of these novel ASMs or combined therapies are rarely reported. Few studies have suggested that levetiracetam (LEV) does not cause clinically significant or relevant hematological disorders(18).

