Such reported side effects may be more significant in pediatric patients with epilepsy due to individual differences in age, weight, and pharmacokinetic action of the body on the drugs. The incidence of coagulopathies has been reported to be higher in children than in adults, especially hypofibrinogenemia(19,20). Nevertheless, whether these coagulation dysfunctions increase the risk of perioperative bleeding remains controversial. Most investigators suggest that ASMs, including VPA, are not associated with surgery-related blood loss or transfusion requirements(21–23). However, a few studies have suggested that considering the extra risk of perioperative bleeding, VPA should be discontinued before surgery(14).

Objectives:

This retrospective analysis of 390 children with epilepsy systematically investigated the incidence and risk factors of preoperative coagulation dysfunction in children undergoing surgery for epilepsy and their impact on surgery, with the objective to provide detailed and valuable clinical information.

Design:

This study was a retrospective cohort study.

Methods:**Study population**

This retrospective study focused on children who underwent surgery for epilepsy between

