January 2015 and December 2021 at the Neurosurgery Department of our hospital. Consecutive patients under 18 years who satisfied the following criteria were enrolled: a discharge diagnosis of "epilepsy" according to the International Classification of Diseases (ICD-10) and surgical treatment during the hospitalization. The following clinical data were collected: sex, age, weight, epilepsy course, and anti-seizure therapy. The initial laboratory data after admission included platelet count (PLT), prothrombin time (PT), activated partial thromboplastin time (APTT), FBG, alanine aminotransferase (ALT), and aspartate aminotransferase (AST). The patients' record of intra/post-operative transfusion or no transfusion was obtained from the medical records. The researchers also collected data on non-epileptic children who underwent non-epilepsy neurological surgery and were admitted at the same period from the Hospital Information System (HIS) as a control cohort. A total of 539 patients were initially included in the study. Patients were excluded if the clinical information or laboratory examinations were incomplete, or had concomitant diseases affecting coagulation or liver function. Patients were also excluded if they refuse to be enrolled to the study. Overall, 390 epilepsy cases and 104 non-epilepsy controls were included in the study (figure 1). All the surgeries were performed by the same surgeon.

ASM therapy

All ASM therapies were administered by a specialist at our hospital and recorded once the patient was admitted. Therapy was defined as the ASMs taken at the time of admission, and all ASM therapies were continued till surgery at our center. Based on the frequency of use of ASMs, drugs taken over 10 times in all cases were included in the statistics, including, VPA, LEV, oxcarbazepine (OXC), carbamazepine (CBZ), topiramate (TPM), and lamotrigine (LTG). Simultaneous administration of two or more types of ASMs was defined as "polytherapy."

Laboratory tests

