Following the clinical routine at our center, routine blood tests, coagulation function tests, and liver function tests were performed after admission. The following laboratory data were collected: PLT, PT, APTT, FBG, ALT, and AST levels. Abnormal coagulation function/coagulation dysfunction/coagulopathy was confirmed if the values obtained were more (or less) than the highest (or lowest) normal range values of either PT, APTT, FBG, or PLT (PT>14.5 s, APTT>45 s, FBG< 2 g/L, PLT<150×10⁹/L). Abnormal liver function was defined as values higher than the highest range of ALT or AST (ALT>42 U/L, AST>59 U/L).

Statistical analyses

Categorical variables are presented as absolute (n) and relative frequencies (%). Continuous variables are shown as the mean (\pm standard deviation) or median (interquartile range), where applicable. The χ^2 test was used to evaluate differences among categorical variables. Continuous variables with normal and skewed distributions were compared using the t-test and Wilcoxon rank-sum test, respectively.

Univariate logistic regression analyses were performed to identify possible determinants of coagulation function. Possible relevant variables were included as covariates for multivariate logistic regression analysis to further filter out distractions. The results of the univariate and multivariate logistic regression analyses are presented as OR and 95% CI. The researchers used

R V4.1.2 to conduct statistical analyses.

Reference

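### Admission haemoglobin is not extracted and no adjusted transfusion model is specified, so a difference in starting haemoglobin could confound the coagulopathy–transfusion comparison and could not be detected

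*Combined protocol and SAP*

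**What the plan says.** The Objectives section sets out to study "risk factors of preoperative coagulation dysfunction in children undergoing surgery for epilepsy and their impact on surgery". For the surgical side, Methods (Study population) offers one outcome: "The patients' record of intra/post-operative transfusion or no transfusion was obtained from the medical records". Blood volume, blood loss, transfusion trigger and type of product are not listed.

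The exposure, in Laboratory tests, is any one of four abnormal results: "PT>14.5 s, APTT>45 s, FBG< 2 g/L, PLT<150×10⁹/L". That section says that "routine blood tests, coagulation function tests, and liver function tests were performed after admission", and then: "The following laboratory data were collected: PLT, PT, APTT, FBG, ALT, and AST levels". The Study population section repeats the same six tests. The other covariates are given there too: "The following clinical data were collected: sex, age, weight, epilepsy course, and anti-seizure therapy". Haemoglobin, haematocrit and anaemia do not appear among the laboratory data, clinical data or exclusions.

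Under Statistical analyses, categorical variables are compared by chi-square test. The univariate and multivariate logistic regressions are for determinants of coagulation function. No regression with transfusion as the outcome is described.

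**The concern.** Whether a child receives red cells depends on the starting haemoglobin as well as on the blood lost. With a yes/no outcome and no blood-loss measure, admission haemoglobin is the variable that would help to tell a child who bled more from one who began with less reserve.

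The Background supplies a possible link to the exposure. Among the reported effects of valproate it lists "bone marrow suppression", beside low platelets and low fibrinogen. Marrow suppression can lower platelets, one of the four coagulopathy criteria, and haemoglobin together. Anaemia is not an exclusion, so anaemic children stay in the cohort.

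At stake is the conclusion on whether preoperative clotting abnormalities matter at surgery, which the Background describes as unsettled. The prevalence and risk-factor objectives are not affected.

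**Working it through.** The plan states no coagulopathy rate, transfusion rate, alpha or effect size, so it has no figure to reproduce. The check asks how large an association could appear when coagulopathy has no effect on transfusion. Except for the 390 epilepsy cases (Study population), every input is an assumption.

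**1. Deficit across the whole coagulopathic group**

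- Haemoglobin is normal with SD 1.3 g/dL. The coagulopathic mean is lower by d = 0.3, 0.5 or 1.0 g/dL.
- Transfusion odds are multiplied by 1.5 or 2.0 per 1 g/dL lower haemoglobin, so the slope is b = ln 1.5 or ln 2.0.
- The risk in children without coagulopathy is p0 = 20% or 40%.
- Let H be the deviation from the non-coagulopathic mean. The individual risk is expit(a − bH). The intercept a is set so that the average over H ~ N(0, 1.3²) equals p0. Then p1 is the average over H ~ N(−d, 1.3²).
- Spurious OR = [p1/(1 − p1)] / [p0/(1 − p0)].

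Example: d = 1.0, odds ×2.0, p0 = 0.20. This gives a = −1.605 and p1 = 0.3144. OR = (0.3144/0.6856)/(0.20/0.80) = 0.4586/0.25 = 1.83.

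**2. Deficit in the low-platelet children only**

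The marrow-suppression route reaches the platelet criterion only. Suppose a fraction f = 10–30% of coagulopathic children carries the deficit. Write p1* for the fully shifted risk from step 1; then p1 = f·p1* + (1 − f)·p0.

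Same example with f = 0.30: p1 = 0.30 × 0.3144 + 0.70 × 0.20 = 0.2343. OR = (0.2343/0.7657)/0.25 = 1.22.

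| Deficit (g/dL) | OR, whole group lower | OR, only 10–30% lower |
|---|---|---|
| 0 | 1.00 | 1.00 |
| 0.3 | 1.12–1.20 | 1.01–1.06 |
| 0.5 | 1.21–1.36 | 1.02–1.10 |
| 1.0 | 1.46–1.83 | 1.04–1.22 |

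**3. Cross-check with anaemia as yes/no**

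Here N = 390, coagulopathy is present in 20% or 40% (78 or 156 children), the risk without anaemia is t0 = 20% or 40%, and the anaemia–transfusion OR is 2 or 4. The group risk is α·t1 + (1 − α)·t0, where α is the anaemia prevalence and t1 the risk with anaemia. The rejection probability is for an uncorrected two-sided chi-square test at an assumed alpha of 0.05.

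Example: t0 = 0.20 and OR 4 give odds of 0.25 × 4 = 1, so t1 = 0.50. With anaemia 30% against 10%, the risks are 0.30 × 0.50 + 0.70 × 0.20 = 0.29 and 0.10 × 0.50 + 0.90 × 0.20 = 0.23. OR = (0.29/0.71)/(0.23/0.77) = 1.37.

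| Anaemia, with vs without coagulopathy | Spurious OR | Rejection probability |
|---|---|---|
| 10% vs 10% | 1.00 | 5.0% |
| 15% vs 10% | 1.04–1.09 | 5.3–6.4% |
| 20% vs 10% | 1.07–1.18 | 5.9–10.6% |
| 30% vs 10% | 1.15–1.37 | 8.6–26.9% |
| 40% vs 15% | 1.19–1.45 | 10.4–37.1% |

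Both models agree: there is no bias when haemoglobin is balanced, and the bias grows with the imbalance. The imbalance is what the planned data cannot show.

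**The case against.** The strongest reply is that the plan contains no coagulopathy–transfusion odds ratio to be confounded. The comparison is implied by the objective and the outcome collected, but it is not written out. Without a transfusion model every covariate is left unadjusted, including age and weight, which are collected. This stands: haemoglobin is one part of a wider gap, and adding the field without specifying the model would not close it.

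Second, nothing in the documents shows lower haemoglobin in coagulopathic children, and the mechanism named reaches one criterion of four. This also stands, and it is why the smaller range in step 2 is given.

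Third, valproate use is recorded, so adjusting for it would deal with part of that pathway, and the exclusion of children with other diseases that affect clotting or the liver removes some shared causes. This is true in part. Marrow suppression can vary among valproate users, and anaemia from other causes remains.

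Fourth, the plan does not say that transfusion means red cells. If plasma or platelets count, starting haemoglobin need not drive those events and the assumed slope would not apply to them. This stands, and the definition needs stating.

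That haemoglobin is on the admission blood count is an inference from the platelet count being there. It is a safe one, but the text does not state it.

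**Conclusion.** The omission is confirmed and the point holds as a possibility. The comparison of coagulopathy with transfusion may be confounded by starting haemoglobin, and the planned data allow neither a check nor an adjustment. The possible size runs from none (OR 1.00, equal haemoglobin), through about 1.02–1.22 (deficit of 0.5–1.0 g/dL in 10–30% of coagulopathic children), to 1.12–1.83 (deficit of 0.3–1.0 g/dL in all of them). The upper end needs a full 1 g/dL deficit averaged over the whole group and the steepest assumed slope; the bias is probably smaller. All these figures take transfusion to be red-cell transfusion.

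A reader might infer that the association is confounded upward, or that any effect found would really be anaemia. The documents support neither, because they give no haemoglobin data. Nor do they show that haemoglobin is the strongest predictor of transfusion, or that its absence costs a known amount of power. It is a plausible major predictor, and that is enough to justify extracting it. The change is worth making because it bears directly on the surgical-impact conclusion and costs little.

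**What to change.** - Add admission haemoglobin to the extraction list, taken from the blood count that supplied the platelet count.
- Specify in Statistical analyses a logistic model with transfusion as the outcome and coagulopathy as the exposure, adjusted for haemoglobin (continuous) and the already collected age, weight and valproate use.
- Report the coagulopathy odds ratio with its 95% CI with and without haemoglobin in that model. Little change would strengthen the conclusion; a clear shift would warn against reading the association as bleeding due to coagulopathy.
- State which blood products count as transfusion.

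Cost: one more field from existing records, one small added model with a short SAP paragraph, and possibly the loss of a few records that lack a haemoglobin value.

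### One fixed laboratory limit per test for every child under 18 may distort the reported prevalence of coagulopathy and blur any age odds ratio, if normal values vary with age

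*Combined protocol and SAP*

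**What the plan says.** The Objectives section says that the study "systematically investigated the incidence and risk factors of preoperative coagulation dysfunction in children undergoing surgery for epilepsy". The outcome behind that aim is defined under Laboratory tests. A child is classed as having coagulopathy when a result lies beyond the "highest (or lowest) normal range values of either PT, APTT, FBG, or PLT", and the limits are listed as "PT>14.5 s, APTT>45 s, FBG< 2 g/L" together with a platelet count below 150×10⁹/L. One abnormal result out of four is enough. The values used are the initial ones after admission, and no repeat test is required.

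The same limits apply to everyone enrolled. Under Study population: "Consecutive patients under 18 years who satisfied the following criteria were enrolled". No lower age limit, age strata or age distribution is given, and the plan does not say in which population the normal ranges were set.

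Age is among the variables recorded: "The following clinical data were collected: sex, age, weight, epilepsy course, and anti-seizure therapy". The Statistical analyses section does not name it as a model term; it says only: "Possible relevant variables were included as covariates for multivariate logistic regression analysis to further filter out distractions". No analysis by age band and no sensitivity analysis on the limits is described. For the four tests, the only continuous comparisons mentioned are the generic t-test and Wilcoxon rank-sum test.

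**The concern.** A fixed limit has the same meaning at every age only if the distribution of normal values is the same at every age. If the normal level of one test moves towards its limit in some age group, more healthy children in that group cross it, and each one is counted as having coagulopathy. A move away from the limit has the opposite effect.

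Two results are exposed. The first is the prevalence, which would then depend on the age mix of the cohort as well as on disease. The second is any OR for age, which would combine normal development with disease in unknown proportions.

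Putting age into the logistic model does not solve either problem. It may help to protect the ORs for anti-seizure medications (ASMs), but a prevalence is not changed by a regression covariate, and the age coefficient is itself the quantity in doubt. The plan does not commit to that adjustment in any case.

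**Working it through.** The plan states no prevalence, OR, power or sample-size figure, so there is nothing of its own to reproduce. What follows is a sensitivity illustration.

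**Inputs from the documents.** Four tests, an any-of-four rule, 390 epilepsy cases and 104 controls.

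**Assumed inputs (not in the documents).**
- Each limit cuts off 2.5% of healthy children in the reference age group.
- The four tests are independent and normally distributed.
- In one age group, the normal mean of one test lies d SD closer to its limit, with d = 0, 0.25, 0.5 or 1.0.
- That age group is half of the cases (195 v 195).
- True disease t is 0% or 20%, the same in both age groups, and diseased children are always flagged.

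**Formulas.**
- Shifted test: p₁ = Φ(−1.96 + d).
- Composite in healthy children, reference group: 1 − 0.975⁴ = 0.096.
- Composite in healthy children, shifted group: f = 1 − (1 − p₁) × 0.975³.
- With true disease: t + (1 − t) × f. For t = 0.20 in the reference group: 0.20 + 0.80 × 0.0963 = 0.277.
- The OR is the ratio of the odds in the two groups; overall prevalence is the mean of the two proportions.

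**Worked case, d = 0.5.** p₁ = Φ(−1.46) = 0.072 and f = 1 − 0.928 × 0.927 = 0.140. The OR is (0.140/0.860) / (0.096/0.904) = 1.53. With t = 0.20: 0.20 + 0.80 × 0.140 = 0.312, and the OR is (0.312/0.688) / (0.277/0.723) = 1.18.

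| Shift (SD) | Shifted test flagged | Group flagged, t = 0 | Age OR | Overall | Group flagged, t = 20% | Age OR | Overall |
|---|---|---|---|---|---|---|---|
| 0 | 2.5% | 9.6% | 1.00 | 9.6% | 27.7% | 1.00 | 27.7% |
| 0.25 | 4.4% | 11.4% | 1.20 | 10.5% | 29.1% | 1.07 | 28.4% |
| 0.5 | 7.2% | 14.0% | 1.53 | 11.8% | 31.2% | 1.18 | 29.5% |
| 1.0 | 16.9% | 22.9% | 2.79 | 16.3% | 38.3% | 1.62 | 33.0% |

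**Chance of p < 0.05 for age, 195 v 195.** With no true disease: 8% / 27% / 95% for the three shifts. With 20% true prevalence: 5% / 11% / 61%.

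**Scale.** At a 30% prevalence, the 95% half-width with 390 cases is 1.96 × √(0.3 × 0.7 / 390) = 4.5 percentage points. With 20% true prevalence, the shift in one test moves the overall figure by 0.7 / 1.8 / 5.3 points (28.4, 29.5 and 33.0 minus 27.7).

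**Control comparison.** With a 1.0 SD shift, no true disease, and 70% of cases but 30% of controls in the shifted age group, 18.9% of cases and 13.6% of controls are flagged although nothing differs but age. With equal age mixes the two figures agree.

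**The case against.** The strongest reply is that the premise is missing. A reader might take the Background as conceding that normal values depend on age, because it says: "The incidence of coagulopathies has been reported to be higher in children than in adults, especially hypofibrinogenemia". That sentence compares how often coagulopathy is reported in children and in adults. It does not say that normal values of these tests move between birth and 17 years, and no section gives a normal value by age. This objection stands: distortion is possible, not demonstrated, and its direction is open.

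A reader might also infer that any age OR would be pure artefact. The documents do not support that either. The Background gives a substantive reason for a real age effect, namely differences in age, weight and drug handling. An age OR could be real, artefactual or mixed. Nor is age certain to be reported as a risk factor, since it is collected but not named in the model.

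The illustration also leans one way. Zero true disease gives the largest ORs, and 20% true prevalence reduces them considerably. The 9.6% baseline comes from applying four tests at once, has nothing to do with age, and falls towards 2.5% if the tests are fully correlated.

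Finally, the limits are disclosed, so the prevalence can be read under that definition, and a concurrent control cohort is judged by the same limits. That partly stands. Controls offset the problem in the case-control comparison if the ages are similar, but no age matching or adjustment is stated, and a comparison with controls does not correct the prevalence in cases.

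**Conclusion.** The concern holds as a conditional one. The text establishes a single limit per test for all patients under 18, an any-of-four rule, no stated source population for the limits, and no age-specific check. It does not establish that the prevalence is wrong or that an age effect would be spurious.

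The possible effect runs from none to large. In the scenarios above, the age OR ranges from 1.00 with no shift to 2.79 with a 1.0 SD shift in one test and no true disease, or 1.62 with 20% true prevalence. These figures rest on assumed shifts, 2.5% tails, independent normal tests and a single shifted test. Because the limits define the outcome named in the objective and the check is cheap, the plan should include it.

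**What to change.** Keep the fixed-limit result, state where the limits come from and in which population they were set, and add:

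1. A sensitivity analysis that reclassifies each test by the hospital laboratory's age-specific limits, where it issues them, with prevalence shown under both definitions.
2. The proportion abnormal by age band, in the epilepsy cases and in the 104 controls.
3. Models of PT, APTT, FBG and PLT as continuous outcomes with age and group (epilepsy v control), so that an age trend shared with controls is not read as an epilepsy or ASM effect.

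Interpret an age OR only if the age association persists in these analyses.

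Limits built from age-specific z-scores in the controls should not become the main definition. Under normality, the standard error of a 2.5% limit estimated from 104 children is about √((1 + 1.96²/2) / 104) = 0.17 SD. The 95% interval is therefore about ±0.33 SD, and wider at the extremes of age. That error is similar in size to the smaller shifts it would be meant to correct.

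The cost is a little more analysis, mainly of data already held. Age bands will be imprecise with 104 controls, and these are neurosurgical patients rather than healthy children. The sponsor must also confirm that age is held for the controls, because the plan lists the variables for the epilepsy patients but refers only to data in general for the control cohort.
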